6.2.1.2. Pharmacodynamic Analysis Set

The pharmacodynamic analysis set will include all subjects who take at least one dose of study drug and have at least one PD parameter measurement at PD baseline (Days -7 to -6) and at least one PD parameter measurement at Day 1 or Day 14. The pharmacodynamic analysis set will be used for all summaries of pharmacodynamic data.

6.2.2. Summary of Analysis Sets

A summary of the number and percentage of subjects included in (and excluded from, as applicable) each analysis set will be provided. The number and percentage of subjects excluded from each analysis set by reason for exclusion will also be provided.

6.2.3. Application of Analysis Sets

Summaries of subject disposition, analysis set inclusion/exclusion status, and Important Protocol Deviations (IPDs) will include all enrolled subjects. All other summaries by analysis set are identified in Table 2.

Table 2: Data Summaries by Analysis Set

	Analysis Set	
Data Summary/Analysis	Safety	Pharmacodynamic
Demographics ^[1]	X	X
Baseline subject characteristics ^[1]	X	X
CAH history	X	
Pharmacodynamic data		X
Plasma concentrations	X	
PK parameters	X	
Adverse events	X	
Clinical laboratory data	X	
Vital signs	X	
Weight	X	
ECG	X	
C-SSRS, Children's Version	X	
BPRS-C	X	

^[1] if the safety analysis set and the pharmacodynamic analysis set are the same, only one set of tables will be created using the safety analysis set.

6.3. Baseline Definitions

6.3.1. Study Baseline

Study baseline will be defined as the last reported value prior to study drug dosing for all safety assessments. The assessments collected at the Day 1 study visit will serve as the baseline value for all assessments. With the exception of C-SSRS, if a Day 1 visit value is not available, then the last measurement collected on or prior to the date of the Day 1 study visit will serve as baseline. C-SSRS values that are missing at Day 1 will remain missing.

6.3.2. Pharmacodynamic Baseline

For all pharmacodynamic data analyses, baseline will be defined as the PD values collected during the 24 hour PD baseline on Days -7 to -6 of the study. The specific timepoints that will be used to represent PD baseline from Days -7 to -6 are further explained in Section 9 of this SAP.

6.4. Derived and Transformed Data

6.4.1. Study Day

Study day is calculated relative to the date of the Day 1 visit. If the date of interest occurs on or after the Day 1 visit, then the study day will be calculated as: date of interest – date of Day 1 visit + 1. If the date of interest occurs prior to the Day 1 visit, then the study day will be calculated as: date of interest – date of Day 1 visit.

6.4.2. Change and Percent Change from Baseline

Change from baseline is calculated as (postbaseline value – baseline value).

Percent change from baseline is calculated as (change from baseline/baseline value * 100).

If either the baseline or postbaseline value is missing, the change from baseline and percent change from baseline will also be missing. The percent change from baseline will also be missing if the baseline value is equal to zero.

6.4.3. Handling of Pharmacodynamic BLQ Data

Pharmacodynamic data with values that are below the limit of quantification (BLQ) will be set equal to the lower limit of quantification (LLQ) unless the value is between two quantifiable measurements, in which case it will be set to missing.

6.4.4. Handling of Early Termination Visit Data

An early termination (ET) visit occurs when a subject discontinues from the study prior to completing the scheduled Day 35 visit. The data collected at ET visits will be included in summary tables and figures if they correspond to a protocol-specified visit or timepoint.

Early termination visit data which are not captured at a protocol-specified visit or timepoint will not be included in by-visit analyses and summaries. They will be included in any analyses that look across all available assessments during the treatment period, including unscheduled visits. They will also be included in any applicable by-subject data listings.

6.5. Handling of Missing Data

6.5.1. Missing Dates

6.5.1.1. Start Dates for Adverse Events and Prior and Concomitant Medications

Missing and incomplete ("partial") dates for adverse events (AEs) and concomitant medications will be imputed for the purpose of estimating the time of the event or medication usage in relationship to study treatment. Any data listings will display the original dates as reported in the database.

The imputation rules for AE start dates are as follows:

• If the date is completely missing, the date will be imputed as the date of the first dose of study drug;

- If only the day is missing, the date will be imputed as the date of the first dose of study drug if the month and year match the month and year of the first dose of study drug; otherwise, the missing day will be imputed as the first day of the month;
- If both the day and month are missing, the date will be imputed as the date of the first dose of study drug if the date is in the same year as the first dose of study drug; otherwise, the missing day and month will be imputed as 01 January;
- If any of the above imputations result in a start date that is later than an existing (not imputed) end date for the event, the start date will be imputed as the end date.

The imputation rules for concomitant medication start dates are as follows:

- If the date is completely missing, the date will be imputed as 01 January in the year of the subject's screening vital signs assessment;
- If only the day is missing, the date will be imputed as the date of the first dose of study drug if the date is in the same month and year as the first dose of study drug; otherwise, the missing day will be imputed as the first day of the month;
- If both the day and month are missing, the date will be imputed as the date of the first dose of study drug if the date is in the same year as the first dose of study drug; otherwise, the missing day and month will be imputed as 01 January;
- If any of the above imputations result in a start date which is later than an existing (not imputed) medication stop date, the start date will be imputed as the stop date.

7. IMPACT OF COVID-19 PANDEMIC

This section describes analyses and summaries that will be produced to help determine the potential impact of the COVID-19 pandemic on the study conduct/data and additional details regarding how data that is potentially impacted by the COVID-19 pandemic will be handled in the analysis plan. It is in alignment with the guidance put forth by the US Food and Drug Administration (FDA; Conduct of Clinical Trials of Medical Products During the COVID-19 Public Health Emergency [March 2020, updated January 2021]) and European Medicines Agency (EMA; Points to consider on implications of Coronavirus disease [COVID-19] on methodological aspects of ongoing clinical trials [March 2020]).

To help understand the impact of the COVID-19 pandemic on the clinical trial data, the following listings will be generated:

- A listing of all subjects affected by the COVID-19 pandemic. The listing will identify subjects who experience at least one of the following situations due to the COVID-19 pandemic (additional situations may be included):
 - o Discontinued study treatment or withdrew from study
 - o Presumed or confirmed diagnosis of COVID-19
 - o Had at least one COVID-19 pandemic-related major protocol deviation
 - o Missed at least one study visit or assessment
 - o Required at least one assessment to be collected using a method other than what is defined in the protocol (eg, remotely)
 - Had at least one known study drug interruption
- A listing of subjects who discontinued study treatment and/or withdrew from study due to the COVID-19 pandemic, which will include the specific reasons.
- A listing by subject of visits and assessments affected by the COVID-19 pandemic (eg, missing, partial, collected remotely).

Further classification and summaries of protocol deviations related to the COVID-19 pandemic are detailed in Section 8.2. All assessments (eg, C-SSRS, BPRS-C) that are collected remotely will be included in the analysis.

Additional summaries may be generated to address the potential impact of the COVID-19 pandemic on the efficacy and safety data, as needed, based on ongoing data review or during the final analysis of study data.

8. STUDY POPULATION

8.1. Subject Disposition

The summary of subject enrollment and disposition will display the number and percentage of subjects who were enrolled, who completed through Day 14 of study drug dosing, and who completed the study (ie, up to Day 35). The number of subjects who did not complete the study will also be summarized, both overall and according to the reason for early discontinuation.

A listing of lot numbers used in the study will be provided.

8.2. Protocol Deviations

Protocol deviations described in the study-specific Protocol Deviation Plan will be entered into the clinical trial management system. Prior to database lock, all major protocol deviations that have been entered into the clinical trial management system will be exported to a file and integrated into the study data.

IPDs are protocol deviations that might significantly affect the completeness, accuracy and/or reliability of the study data or that might significantly affect a subject's rights, safety, or well-being. An assessment of IPDs will be performed by a committee composed of NBI Clinical Development project team members prior to database lock. This committee will review a listing of all major protocol deviations reported in the study database and determine which deviations are IPDs.

A summary of the number and percentage of subjects with IPDs by deviation category will be provided using all enrolled subjects. The summary will be repeated for the subset of IPDs that are related to the COVID-19 pandemic.

[figure not shown]
All major protocol deviations will be presented in a data listing and any that are classified as IPDs will be flagged in the listing. Any major PDs related to the COVID-19 pandemic will also be flagged in the listing.

8.3. Demographic and Baseline Characteristics

Demographic and baseline characteristics data will be summarized using descriptive statistics.

Demographics include:

- Age (years)
- Sex
- Ethnicity
- Race

- 17-OHP levels at screening
- Body surface area (BSA; calculated using the DuBois formula and height collected at the screening visit and weight collected at the Day 1 visit; m²)

- Total daily glucocorticoid dose at screening, expressed in hydrocortisone equivalents (mg/day) (See Table 5)
- Total daily glucocorticoid dose at screening, expressed in hydrocortisone equivalents (See Table 5) and adjusted for BSA (mg/m²/day)
- Glucocorticoid type (hydrocortisone alone; prednisone or equivalent with or without hydrocortisone; dexamethasone with or without another glucocorticoid)
- Height (measured at screening; cm)
- Weight (presented in both pounds and kilograms)
- Body mass index (BMI; calculated using height collected at the screening visit and weight collected at the Day 1 visit; kg/m²)

8.4. CAH History

CAH history will be summarized using descriptive statistics.

CAH history assessments include:

- How the CAH diagnosis was made
- Number of adrenal crises within the past 2 years
- Age at menarche (female subjects only)
- Menstrual cycle frequency (in days; female subjects only)

9. PHARMACODYNAMIC DATA

PD biomarker data include measurements of ACTH, 17-OHP, androstenedione, testosterone, and cortisol. Note that all summaries of testosterone will be stratified by sex. The following sections describe the summaries and analyses of the PD biomarker data.

9.1. Timepoint Summaries

Observed values for the PD biomarker data will be summarized with descriptive statistics by parameter, visit, and timepoint. This summary will also include the changes from PD baseline to postdose values with the same timepoint (eg, change from Day -7/-6, 6 hours post-evening dose to Day 14, 6 hours post-evening dose). Descriptive statistics for the 24 hour average values of the PD parameters at each visit (excluding Day 7 and Day 21) will also be displayed. Figures of mean (+SE) versus time curves will be generated for each parameter by visit. In addition, these data will be displayed as individual subject observed values versus time curves for each parameter by visit.

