12.3. Handling of Missing Data

All available study data will be included in relevant summaries and data displays, including any available data for subjects with incomplete or missing data.

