4. STUDY DESIGN

4.1. Summary of Study Design

This is a Phase 2, open-label, multiple-dose study to assess the safety, tolerability, PK, and PD of crinecerfont in approximately 12 pediatric female and male subjects (14 to 17 years of age) with a documented medical diagnosis of classic 21-hydroxylase deficiency CAH. Crinecerfont 50 mg bid will be administered for 14 consecutive days with breakfast and evening meals beginning on the evening of Day 1.

[figure not shown]
Eligible subjects who have a screening 17-OHP level ≥800 ng/dL will be admitted to the study center on Day -7 for 1 night and have baseline serial PD samples collected over a 24-hour period beginning that evening. Baseline serial PD samples will be collected at approximately 1845, 2000, 2300, 0100, 0300, 0700, 1000, 1500, and 1900 hours.

The subjects' usual morning dose of steroidal treatments will be administered after the 1000 hours PD sample is collected on Day -6. Subjects will be discharged on Day -6 after the last PD sample is collected.

Subjects will be admitted to the study center on Days 1 and 14 (first and last day of dosing). The first dose of study drug, crinecerfont 50 mg, will be administered at approximately 1900 hours with subjects' evening meal on Day 1. Study drug will be administered at the study center on Days 2 and 14 with subjects' breakfast and evening meals, respectively. The subjects' usual morning dose of concurrent steroidal treatments, study drug dosing, and breakfast (snacks will be allowed prior to breakfast) will be delayed until after the 15-hour postdose PD samples are collected (ie, at approximately 1000 hours) on Day 2. The subjects' usual morning dose of concurrent steroidal treatments will be administered after the 15-hour postdose PD samples are collected (ie, at approximately 1000 hours) on Day 15. Study drug will be self-administered at home under parent/guardian supervision at approximately 0700 hours (with breakfast) and 1900 hours (with evening meal) on Days 3 to 13.

The study design schematic is shown in Figure 1.

Figure 1: Study Design Schematic

bid=twice daily; ET=early termination; PD=pharmacodynamic; NBI-74788=crinecerfont.

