9.2. Morning Window Summaries

The peak morning period for ACTH, 17-OHP, androstenedione, and testosterone levels is between 0700 and 1000 hours. For the purposes of analysis, this timeframe will be referred to as the "morning window" and includes all PD biomarker measurements (excluding cortisol) taken during this time. Specifically, the morning window timepoints for PD draws are 12- and 15-hours post-evening crinecerfont dose. This group of timepoints will be summarized using the average of the two morning window timepoints at each visit. If only one timepoint is available, this value will be used as the morning window value. If both timepoints are missing, the morning window value for that subject/visit will be reported as missing.

The morning window values will be summarized with descriptive statistics by PD parameter and visit. In addition to the observed values, descriptive statistics will also be generated for the change from PD baseline to Day 1 and from PD baseline to Day 14, as well as the percent change from PD baseline to Day 1 and from PD baseline to Day 14. Percent change from PD baseline to Day 1 and Day 14 for each subject will be presented as waterfall plots by PD parameter.

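### The PD 24-hour average should be time-weighted, and BLQ values lying between quantifiable ones should not be deleted from PD summaries

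*SAP*

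**What the plan says.** SAP 9.1 lists, beside the timepoint summaries, "Descriptive statistics for the 24 hour average values of the PD parameters at each visit", leaving out Days 7 and 21. That leaves PD baseline, Day 1 and Day 14. No formula or weighting is given there or among the derived variables in SAP 6.4.

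The samples come from a fixed schedule. SAP 4.1 states: "Baseline serial PD samples will be collected at approximately 1845, 2000, 2300, 0100, 0300, 0700, 1000, 1500, and 1900 hours". SAP 6.1 defines the Day 1 and Day 14 windows as running from 15 minutes before the evening dose to 24 h after it, and the protocol's PD schedule puts the samples at the same clock times.

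SAP 9.2 says of the daily pattern: "The peak morning period for ACTH, 17-OHP, androstenedione, and testosterone levels is between 0700 and 1000 hours". It defines its own summary as the average of the 12 and 15 h samples.

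SAP 6.4.3 sets PD values below quantification to the LLQ "unless the value is between two quantifiable measurements, in which case it will be set to missing".

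**The concern.** An average described as covering 24 hours should represent the day. A plain mean of unevenly spaced samples represents the sampling scheme instead. Here sampling is densest in the evening and night and sparsest from 1000 to 1900 h. The plan itself states a morning peak for four of its five analytes, so levels are not expected to be flat.

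The BLQ rule works on the same quantity. A value below quantification is known to be low. Deleting it when it lies between higher values, while keeping it at the LLQ elsewhere, raises whatever average it would have entered. If low values are commoner on treatment than at PD baseline, the rule would blunt the apparent reduction.

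**Working it through.** The plan states no figure for this average, so there is none to reproduce.

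**Step 1: weights, from the schedule alone.** Taking 1900 h as time 0, the samples fall at -0.25, 1, 4, 6, 8, 12, 15, 20 and 24 h, a span of 24.25 h. A plain mean weights each 1/9 = 11.1%. The linear trapezoid weights an interior sample by half the distance between its neighbours, divided by 24.25. An end sample gets half its single gap, divided by 24.25.

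| Sample (h) | -0.25 | 1 | 4 | 6 | 8 | 12 | 15 | 20 | 24 |
|---|---|---|---|---|---|---|---|---|---|
| Hours represented | 0.625 | 2.125 | 2.5 | 2 | 3 | 3.5 | 4 | 4.5 | 2 |
| Trapezoid weight (%) | 2.6 | 8.8 | 10.3 | 8.2 | 12.4 | 14.4 | 16.5 | 18.6 | 8.2 |

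- First five samples: 5/9 = 55.6% plain; 10.25/24.25 = 42.3% time-weighted.
- The 12 and 15 h samples: 2/9 = 22.2% plain; 7.5/24.25 = 30.9% time-weighted.

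**Step 2: effect on the average, under assumed profiles.** The documents give no PD values, so these are illustrations (ng/dL, in sample order).

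- Low afternoon: 300, 300, 600, 1500, 3000, 6000, 6000, 800, 300. Plain 18,800/9 = 2,089; trapezoid 63,525/24.25 = 2,620. The plain mean is 20.3% lower.
- Intermediate: 1000, 1000, 1500, 2500, 4000, 6000, 6000, 2000, 1000. Plain 25,000/9 = 2,778; trapezoid 79,500/24.25 = 3,278. The plain mean is 15.3% lower.
- Flat: equal.

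A second family sets off-peak values to 1, the 12 and 15 h values to R, and the 8 h value to (1+R)/2. The plain and time-weighted means are 1.278 and 1.371 (R = 2), 1.833 and 2.113 (R = 4), and 2.944 and 3.598 (R = 8). The plain mean is about 7%, 13% and 18% lower.

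**Step 3: effect on percent change.** If every value falls by the same proportion, both formulas give the same percent change. If only the 8, 12 and 15 h values fall by 50%, the plain and time-weighted averages change by -23.9% and -29.3% (R = 2), -31.8% and -36.6% (R = 4), and -38.7% and -42.1% (R = 8).

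**Step 4: direction and size of the BLQ rule.** Let m be the mean of the other eight values and L the LLQ. Each of the eight is quantifiable or set to L, so m is at least L. Keeping the BLQ value at L gives (8m + L)/9; deleting it gives m. The relative rise is (m - L)/(8m + L), which is never negative and stays below 1/8 = 12.5% for one deletion. A trapezoid that bridges the gap is likewise raised or unchanged, because the line between the two neighbours lies at or above L.

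Take the low-afternoon profile with the 20 h value BLQ and an assumed LLQ of 50. The plain mean goes from 18,050/9 = 2,006 to 18,000/8 = 2,250 (+12.2%). The bridged trapezoid goes from 60,150/24.25 = 2,480 to 72,675/24.25 = 2,997 (+20.8%). With an LLQ of 10 or 100 the rises are +12.4% or +11.9% plain, and +21.2% or +20.4% bridged. If one of 12 similar subjects is affected, the group mean moves by about 12.2/12 = 1.0% or 20.8/12 = 1.7%.

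**The case against.** The best defence is that a plain mean is a legitimate descriptive choice. SAP 9.2 averages that way, the SAP names AUC where it means AUC, and applying one method at every visit keeps comparisons fair. Step 3 supports this for a uniform proportional fall, but not for an effect concentrated in the morning. It is also true that the percentages in Steps 2 to 4 rest on invented profiles and an assumed LLQ. The weights in Step 1 and the direction in Step 4 do not.

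For the BLQ rule, one can say that an isolated low reading between quantifiable ones may be an assay fault, and SAP 10.2 treats PK concentrations that way. But PD sampling straddles the steroid dose at about 1000 h, so a low value between two higher ones is not implausible in itself.

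Three stronger readings are tempting and are not supported:

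- **That missing samples have no rule, so a lost peak sample could pass for a drug effect.** Protocol 12.3 keeps all available data, "including any available data for subjects with incomplete or missing data". What is absent is detail, such as a minimum number of samples.
- **That the PD baseline timepoints are undefined because SAP 6.3.2 says they "are further explained in Section 9 of this SAP".** SAP 6.3.2 itself takes the values from the 24-hour baseline, and SAP 4.1 lists all nine times.
- **That the Day 14 average misleads because its window holds only one study drug dose.** Protocol Table 1 does show one dose in that window, and doses at 0 and 15 h in the Day 1 window. But SAP 4.1 and 6.1 already give these facts, and Section 9 compares each visit only with PD baseline. The Day 14 morning dose comes about 12 h before the window's evening dose. The public text gives no half-life or PD offset from which an understatement could be shown. Protocol 9.3, read literally as 14 full days after an evening start, could reach the morning of Day 15. That wording and Table 1 should be reconciled.

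**Conclusion.** Two concrete weaknesses hold, and both are minor. First, a plain mean on this schedule misweights the day: 56% against 42% for the samples through 8 h, and 22% against 31% for the morning peak. It equals the time-weighted value on a flat profile and falls up to about 20% below it on the assumed peaked ones. This rests on reading the undefined average as a plain mean. Second, the BLQ rule can only raise PD averages or leave them unchanged. The rise is below 12.5% for one deletion from a nine-sample plain mean, and about 20 to 21% for a bridged trapezoid on one assumed profile.

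Nothing is tested and the sample is about 12 subjects. Individual timepoints and curves are reported alongside. The responder, waterfall and PK/PD outputs use the morning window, so the choice of formula does not touch them. The BLQ rule could reach them only if a deleted value fell at 12 or 15 h, since SAP 9.2 then says "If only one timepoint is available, this value will be used as the morning window value".

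**What to change.** 1. In SAP 9.1, define the 24-hour average as the linear-trapezoid AUC over the sampled interval divided by the elapsed time. Use actual sampling times and the same method at PD baseline, Day 1 and Day 14.
2. In SAP 6.4.3, set BLQ values between quantifiable values to the LLQ, like other BLQ values. Apply this in all PD summaries so that timepoint rows, curves and averages agree.

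The cost is two edited sentences and minor programming, with no new samples or visits. LLQ substitution slightly overstates very low values.

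The trapezoid is also not more robust to every missing sample. On the low-afternoon and intermediate profiles, losing the 12 h sample moves it by -7.1% and -3.8%, against -23.4% and -14.5% for the plain mean. Losing the 20 h sample moves it by +14.4% and +6.9%, against +7.7% and +3.5%. No limit on interpolation gaps is needed. Nor is a rule that voids the whole average when the predose sample, with 2.6% of the weight, is absent: averaging over the remaining 23 h moves the result by +4.8% (63,150/23 = 2,746) or +3.8% (78,250/23 = 3,402). A footnote on the Day 14 dosing pattern is optional.
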